## 1.0 Objectives / Specific Aims

### **Aim 1: Test a home based taVNS protocol for feasibility and efficacy in NeuroCovid patients.**

We will recruit 30 formerly COVID positive adults (ages 18-70) in order to have 24 completers. We will enroll subjects who had a definite case of COVID (were antigen positive) and are at home and are no longer in the hospital. They must also have a residual neuropsychiatric symptom(s) that started anew after COVID developed (NeuroCovid). We will refer to these subjects as 'initially neurocovid and persisting'. We will also enroll those who were asymptomatic, were tested as COVID positive, and then developed NeuroCovid symptoms shortly after their testing. We call these subjects 'initially asymptomatic with later Neurocovid'. (There are several Covid diseases which occur after the acute illness has passed, particular hypercoagulable states and thrombotic strokes and heart attacks.) Symptoms we will target include anxiety, depression, and other CNS symptoms (e.g., vertigo, anosmia, headaches, fatigue, irritability, cognitive processing, etc.). Subjects will be recruited from MUSC electronic records and local testing centers, with online phone screens, consents and ratings. This study is pioneering in being entirely online and home-based. We will provide telemedicine-based device-use support on demand. There will be two experimental groups – initial active taVNS and initial sham stimulation. Subjects will be randomly assigned to each group for a two-week in-home intervention of two hours per day for six days per week of stimulation (active or sham). After the controlled 2-week period, all participants will continue in a 2-week open label arm. Outcomes will include vital signs recorded through the device, mood ratings and a cognitive battery assessing neuropsychiatric functioning and symptoms. These online ratings will be obtained at baseline, taVNS treatment weeks 1-4, and 2-, 4-, 6-, and 8- weeks after treatment. We will also assess feasibility and tolerability. The device will collect daily subjective patient data as well as heart rate, blood pressure and respiration during the treatments.

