### **Aim 2: Test whether 2 or 4 weeks of stimulation differ.**

At the end of two weeks, all subjects will receive two more weeks of intervention, with all receiving active stimulation without breaking the blind. This has two purposes. First, all subjects will eventually receive active treatment, aiding IRB approval and recruitment. Second, it will examine two versus four weeks of stimulation.

This work will provide pilot data for a subsequent clinical trial application to test at home taVNS technology for specific NeuroCovid symptoms. Importantly, the data gained on device efficacy and in-home feasibility for NeuroCovid applications can be readily applied to a number of post-COVID disabilities and rehabilitation needs (e.g., COPD and other complications treated through immunomodulatory and respiratory therapy amenable to vagal nerve action). We strongly believe this technology has great potential for treating those currently sick with or disabled by COVID. We simply don't know what is in store one year from now, but it is likely that the aftershocks of this pandemic will be the defining backdrop of the next decade. A strength of this proposal is that it will allow us to pivot in the directions of greatest need in one year with a multitude of potential therapeutic targets and benefits, once initial feasibility and efficacy of the taVNS home therapy protocol has been established. The research team is experienced and are leaders in neuromodulation research and are thus uniquely capable of successfully shepherding this pilot work into a funded clinical trial.

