##### Primary Outcome:

As this is a pilot and exploratory study, the outcomes are largely descriptive. In terms of feasibility we will assess dropout rates and compliance and subjective ratings of the device and the online only study. In terms of safety we will assess changes in blood pressure and any syncope or other adverse events. We will also examine changes in neuropsychiatric symptoms for patients presenting with different NeuroCovid symptoms.

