**6.0 Number of Subjects**

We will recruit 30 COVID positive adults in order to have 24 completers.

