## **12.0 Data Management**

All data will be stored in the Redcap database. The blind will be kept by the MUSC RA, but they will be blinded as well. Soterix will set the active or sham control from the company after being instructed by the MUSC RA about the randomization code number for that patient, but MUSC will have the unblind in terms of emergency.

Information about the participant (including their identifiable private information and/or any identifiable biospecimens) may have all of their identifiers removed and used for future research studies or distributed to other researchers for future research without additional informed consent from them or their legally authorized representative.

In rare cases, the device manufacturer, Soterix, may need access to minimal PHI (such as name, phone number and address) in the event there is a device malfunction. Well-trained MUSC staff will make every attempt to resolve any issues before putting Soterix in direct contact with the participant.

At a high-level analysis, we will compare the group changes in neuropsychiatric questionnaires in active versus sham taVNS using repeated measures ANOVA from baseline to immediately after last treatment and then as well over the 3-month follow-up.

Power analysis on primary outcome: As there is no real data yet on taVNS effects on NeuroCOVID patients, it is difficult to perform a formal power analysis. The repeated measures design in 15 active and 15 sham patients will allow us to detect differences with a large or moderate effect size to be used for calculating power and sample size for subsequent trials.

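### The active-sham comparison uses change from baseline with no baseline covariate; adjusting for the baseline score already collected would usually give a modestly more precise estimate at almost no cost.

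*Combined protocol and SAP*

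**What the plan says.** The only efficacy analysis statement is in section 12.0 (Data Management). It will "compare the group changes in neuropsychiatric questionnaires in active versus sham taVNS using repeated measures ANOVA". The comparison is made "using repeated measures ANOVA from baseline to immediately after last treatment and then as well over the 3-month follow-up". Baseline enters as the first time point of the change. No covariate, ANCOVA or baseline-adjusted mixed model is named anywhere.

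The baseline score will be available. Aim 1 says: "These online ratings will be obtained at baseline, taVNS treatment weeks 1-4, and 2-, 4-, 6-, and 8- weeks after treatment".

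On size, section 6.0 says: "We will recruit 30 COVID positive adults in order to have 24 completers". Section 12.0 puts 15 patients in each arm and says that the differences detected are "to be used for calculating power and sample size for subsequent trials". The Primary Outcome paragraph of section 4.0 limits the ambition: "As this is a pilot and exploratory study, the outcomes are largely descriptive".

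On timing, Aim 1 states: "After the controlled 2-week period, all participants will continue in a 2-week open label arm". Aim 2 confirms that after two weeks "all subjects will receive two more weeks of intervention, with all receiving active stimulation".

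**The concern.** With one baseline and one later rating, the group-by-time test in a repeated measures ANOVA is the two-sample t-test on change scores. That test subtracts the whole baseline score, as if each extra point at baseline carried forward as a full point later. Usually the slope is below 1, and subtracting everything then adds noise. It also over-corrects for chance imbalance. With 12 per arm, the baseline difference between arms has a standard error of √(2/12) = 0.41 SD. If the true slope is 0.5, an imbalance of that size moves the change-score estimate by (1 − 0.5) × 0.41 = 0.20 SD. Such shifts average to zero over randomisations, so they appear as lost precision rather than bias.

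What is at stake is the width of the interval around an effect estimate that is meant to help plan later trials. A second matter affects what is estimated. Both contrasts named in section 12.0 end after the initial sham arm has received active stimulation, so neither is the sham-controlled effect.

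**Working it through.** **The plan's own figure.** Section 12.0 says that 15 per arm can detect a large or moderate effect. It gives no significance level, power, SD or correlation, so this cannot be reproduced. Recruiting 30 for 24 completers is consistent with 20% loss: 24/(1 − 0.20) = 30.

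**Inputs.** From the documents: N = 24 completers. Assumed: equal loss (12 per arm), baseline SD = 1, follow-up SD = s times baseline, and baseline-to-follow-up correlation r. The documents give neither s nor r, so both are varied.

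**Formulas, one follow-up visit.**
- Change score: variance = (2/12)(1 + s² − 2rs); for s = 1 this is (2/12) × 2(1 − r).
- Baseline-adjusted: variance = (2/12) s²(1 − r²)(1 + 1/(N − 4)). The last factor, 1.05 at N = 24, is the price of estimating the slope.
- Ratio (adjusted/change) for s = 1: (1 + r)/2 × 1.05.

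**Equal SDs, N = 24.** Half-widths are for 95% intervals in SD units, using t with 22 df (change) and 21 df (adjusted). The last column, 24/ratio, is the number of completers a change-score analysis would need to match 24 adjusted ones.

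| r | SE change | SE adjusted | Variance ratio | Half-width change → adjusted | Completers to match |
|---|---|---|---|---|---|
| 0.3 | 0.483 | 0.399 | 0.683 | 1.00 → 0.83 | 35.2 |
| 0.5 | 0.408 | 0.362 | 0.788 | 0.85 → 0.75 | 30.5 |
| 0.7 | 0.316 | 0.299 | 0.892 | 0.66 → 0.62 | 26.9 |
| 0.8 | 0.258 | 0.251 | 0.945 | 0.54 → 0.52 | 25.4 |
| 0.9 | 0.183 | 0.182 | 0.997 | 0.38 → 0.38 | 24.1 |

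Simulation of the same setting (40,000 runs per cell) gave ratios of 0.684, 0.785, 0.897 and 1.000 at r = 0.3, 0.5, 0.7 and 0.9.

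**Break-even, equal SDs.** Setting the ratio to 1 gives r = 2/(1 + 1/(N − 4)) − 1. This is 0.905 at N = 24 and 0.926 at N = 30. At N = 10 it is 2/(7/6) − 1 = 0.71.

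**Unequal SDs, N = 24.**
- s = 1.1, r = 0.8: change 1.21 + 1 − 1.76 = 0.450; adjusted 1.21 × 0.36 × 1.05 = 0.457; ratio 1.016. Break-even is at r of about 0.77.
- s = 1.3, r = 0.7: change 1.69 + 1 − 1.82 = 0.870; adjusted 1.69 × 0.51 × 1.05 = 0.905; ratio 1.04.
- s = 0.7, r = 0.5: change 0.49 + 1 − 0.70 = 0.790; adjusted 0.49 × 0.75 × 1.05 = 0.386; ratio 0.49.

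**Why the loss is capped.** The change-score term 1 + s² − 2rs equals s²(1 − r²) + (1 − rs)². The ratio therefore cannot exceed 1 + 1/(N − 4), and reaches it only when the slope rs equals 1. The cap is 5% at N = 24. At N = 10 it is 1/6, about 17%.

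**Timing.** Ratings at treatment weeks 1 and 2 fall within the sham-controlled period. Ratings from week 3 on compare four weeks of active stimulation with two weeks of sham followed by two of active. The totals in section 10.0 say the same: up to 48 hours of active treatment in one arm and 24 in the other.

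**The case against.** The strongest reply is that the gain depends on quantities the plan does not give and may be small. At r = 0.7 to 0.8 the half-width shrinks by only 0.02 to 0.04 SD, which would change no conclusion in a descriptive pilot. Section 12.0 offers only a high-level analysis, so silence about a covariate is not a decision against one. The SDs and correlation needed to size a later trial can be computed from the stored scores whichever model is fitted. All of this stands and keeps the point modest.

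A reader might infer that adjustment wins whenever the correlation is below about 0.9. That needs equal SDs and about 24 analysed patients. A larger follow-up SD lowers the threshold. So would analysing a questionnaire only in patients with the matching symptom, which section 4.0 may intend; the subgroup sizes are not stated. What survives is the asymmetry at N = 24: a possible gain of 20% to 30% of variance at low to middle correlations (equal SDs), against a loss of at most about 5%.

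A reader might also infer that week 2 is the only blinded active-sham comparison. The documents do not support that. Aim 1 also schedules a week-1 rating, and Aim 2 says that the blind is kept in the second phase, although Aim 1 calls that phase open label. What clearly ends at week 2 is the sham control.

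**Conclusion.** The point holds as a modest efficiency loss. With equal SDs and 24 completers split evenly, adjusting for baseline lowers the variance of a single-visit active-sham difference by about 32% at r = 0.3, 21% at 0.5, 11% at 0.7 and 5% at 0.8, with essentially no gain at 0.9. A smaller follow-up SD makes the gain larger. A larger one can turn it into a loss, of up to about 5% at this size and more in small subgroups. Intervals stay wide under either analysis at low to middle correlations.

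A reader might take this to mean that the planned analysis is biased or that a confirmatory test fails. Neither follows: under randomisation the change score is unbiased, and the plan declares no confirmatory test. The case for changing it is that the covariate is already collected and the estimate is meant to inform later trials.

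**What to change.** In section 12.0, state that post-baseline questionnaire scores will be analysed with the baseline score of the same questionnaire as covariate. Use ANCOVA for a single visit. For repeated visits, use a mixed model with arm, week, arm-by-week and baseline score, a simple covariance structure such as compound symmetry, and a small-sample degrees-of-freedom correction.

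Report the active-sham difference at week 2, the end of the sham-controlled period; the week-1 difference is also sham-controlled and can be shown beside it. Label every contrast after week 2 *initial active versus initial sham*. The week-2 rating is on the Aim 1 schedule, but section 4.0 lists different times, so the two lists should be reconciled.

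The cost is a few sentences of analysis wording and standard software, with no new data. The price is one degree of freedom, and no gain, or a loss of up to about 5% of variance at 24 completers, if the baseline slope is near 1. For any questionnaire analysed only in a small symptom subgroup, state the number analysed, because the possible loss there is larger.

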## 3.0 Intervention to be studied

We will be using the Soterix Medical Handheld home based taVNS device. Our group has been using taVNS in a variety of clinical laboratory, office or ICU based studies, most of them monitored through this IRB. This is the first MUSC protocol using home based taVNS.

The Soterix device is a research device that is FDA cleared in terms of safety but is not FDA approved for any indication. More information can be found here.

<https://soterixmedical.com/research/tavns>

This IRB and most others have found that taVNS is a minimal risk device and does not require an FDA IDE.

We have attached the device specifications from the manufacturer.

- Cervical VNS is FDA approved for medication resistant epilepsy as well as medication resistant depression (Livanova). FDA pivotal trials are underway for paired cervical VNS with rehab for stroke (microtransponder). Noninvasive

cervical VNS is FDA approved for treating cluster headache (electrocore). To date there are no FDA approved indications for taVNS.

- We will use the device twice daily, six days/week for an initial 2-week double blind phase followed by an additional two weeks active open phase. Thus, subjects will get 24 or 48 actual sessions over 4 weeks. Those randomized to active during the first two weeks will get twice as much overall taVNS as those who get sham during the first two weeks (*25Hz, 500us pulse width, 60s ON, 30s OFF, 1 hr. duration per session*). Subjects will be given a training video to watch and will then have an online training session with the MUSC RA. They will be instructed how to administer the device. For the first 3 sessions at least, the RA will be online watching them do this. They will prepare a checklist of how well the subject is doing the treatment. The patient can then only administer the treatment alone if they are checked off. Treatments will be monitored online for as long as it takes for the participant to be checked off.
- Active stimulation will be in the proper location in the ear. Sham stimulation will be in the same location but there will be a small ramp up of the device, delivering stimulation for 20 seconds, and then it will be programmed to turn off, until the end of the session when it will turn on again for 20 secs.

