#### 4.0 Study Endpoints

Outcomes will include vital signs, mood ratings and a cognitive battery assessing neuropsychiatric functioning and symptoms, and will be obtained at baseline, 2, 3, 4, 5, 6, 8 and 12 weeks after treatment. We will also assess feasibility and tolerability.

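### The active-versus-sham analysis in section 12.0 runs past week 2, when the sham arm switches to active, and never names the sham-controlled week-2 contrast

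*Combined protocol and SAP*

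**What the plan says.** **Treatment.** Section 1.0, Aim 1 limits the sham comparison to two weeks: "After the controlled 2-week period, all participants will continue in a 2-week open label arm". Aim 2 describes the same switch, "with all receiving active stimulation without breaking the blind", and gives as its second purpose "Second, it will examine two versus four weeks of stimulation". Section 3.0 states the resulting exposure: "Thus, subjects will get 24 or 48 actual sessions over 4 weeks". Section 10.0 agrees (24 double-blind sessions, then 24 more for everyone), as does section 16.0. Section 18.0 has the device returned after four weeks.

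**Analysis.** Section 12.0 compares "active versus sham taVNS using repeated measures ANOVA from baseline to immediately after last treatment and then as well over the 3-month follow-up". It does not define the last treatment or list the time points in the model. Its power paragraph says the resulting effect size will be used to plan later trials. Under the outcome headings of section 4.0 no time point is given, and the primary outcome is introduced with "As this is a pilot and exploratory study, the outcomes are largely descriptive". No analysis is written for Aim 2.

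**Ratings.** Aim 1: "These online ratings will be obtained at baseline, taVNS treatment weeks 1-4, and 2-, 4-, 6-, and 8- weeks after treatment". Section 4.0: "will be obtained at baseline, 2, 3, 4, 5, 6, 8 and 12 weeks after treatment". Section 10.0 has weekly assessments, plus weeks 4, 6, 8 and 12 counted from study start.

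**The concern.** An active-versus-sham comparison needs one arm on sham. After week 2 neither arm is. What remains is a valid randomised comparison of an immediate with a delayed start, but it answers a different question from the one its label states.

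Two things are at stake. First, a significant group-by-time result could be reported as an active-versus-sham effect when the arms did not differ under sham control; equally, a real two-week effect could be obscured because the sham arm later caught up. Second, the effect size carried into later trials would not be tied to a defined contrast, and the week-2 and week-4 values can differ in either direction.

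**Working it through.** **1. Align the windows with treatment.** Sessions: 2 per day × 6 days × 2 weeks = 24; over 4 weeks, 48.

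| Time | Initial active: active sessions | Initial sham: active sessions | What the arms compare |
|---|---|---|---|
| End of week 2 | 24 | 0 | Active v sham |
| End of week 4 (last treatment) | 48 | 24 | Four v two active weeks |
| Follow-up | 48 | 24 | Four v two active weeks |

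Section 12.0 names the second and third rows and calls both active versus sham. Keeping allocation masked after week 2 does not change this, because no one is then on sham.

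**2. Sham-controlled share of post-baseline ratings.**
- Aim 1 schedule: weeks 1 and 2 out of weeks 1, 2, 3, 4, 6, 8, 10, 12, so 2 of 8.
- Section 10.0, if weekly covers weeks 1–4: 2 of 7.
- Section 4.0 read as study weeks: 1 of 7.
- Section 4.0 read literally, counting from the end of treatment at week 4: study weeks 6, 7, 8, 9, 10, 12, 16, so 0 of 7. Aim 1 and section 10.0 contradict this reading.

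**3. How the late contrast relates to the week-2 contrast.** Let Δ be the active-minus-sham difference in change from baseline. Then

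Δ(week 4) = Δ(week 2) + (active-arm gain, weeks 2–4) − (sham-arm gain, weeks 2–4).

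The late contrast is smaller if the sham arm gains more after the switch, equal if the gains match, and larger if benefit needs more than two weeks.

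**4. The plan's own figures.** Recruitment is consistent: 24/(1 − 0.20) = 30, with 20% dropout implied by 24 of 30. The statement that 15 per arm can detect a large or moderate effect gives no alpha, power, numerical effect or time point, so it cannot be reproduced.

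**5. Illustration; every trajectory and correlation is assumed.** Group-by-time F test, compound symmetry, unit variance, correlation r = 0.6, n = 12 completers per arm, two-sided 5%, ratings at weeks 0, 1, 2, 3, 4, 6, 8, 10, 12. With D the arm difference at each of T ratings, the noncentrality is (n/2) × Σ(D − mean D)²/(1 − r), on T − 1 and (T − 1)(2n − 2) degrees of freedom. Example, weeks 0 and 2 with D = (0, 0.8): sum of squares 0.32, noncentrality 6 × 0.32/0.4 = 4.8, power 55%.

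Except in the late-only case, D is 0.4 at week 1 and 0.8 at week 2. In the plateau cases the active arm is flat from week 2.

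| Case | Weeks 0, 2 | Weeks 0, 4 | Weeks 0–4 | All nine |
|---|---|---|---|---|
| Plateau, sham arm catches up fully by week 4 | 55% | 5% | 50% | 57% |
| Plateau, sham arm catches up half | 55% | 18% | 40% | 30% |
| Plateau, no catch-up | 55% | 55% | 56% | 54% |
| Linear gain per active week in both arms | 55% | 55% | 56% | 54% |
| Late-only: D = 0 to week 2, 0.4 at week 3, 0.8 from week 4 | 5% | 55% | 56% | 86% |

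Over weeks 0–4, D = (0, 0.4, 0.8, 0.8, 0.8) and D = (0, 0, 0, 0.4, 0.8) both have sum of squares 0.512, noncentrality 7.68 and 56% power. The second has no effect while sham is in use.

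Sensitivity, plateau with half catch-up, same column order: d = 0.5, r = 0.6 gives 26 / 10 / 17 / 13%; d = 0.8, r = 0.8 gives 84 / 32 / 72 / 60%; d = 0.8, r = 0.6 with 15 per arm gives 66 / 22 / 49 / 38%.

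**6. Effect on a later trial.** Two-sample t test on change scores, 80% power, two-sided 5%, change SD = √(2(1 − r)). At r = 0.6 (SD 0.894), 0.8 needs 21 per arm and 0.4 (the half catch-up value at week 4) needs 80. At r = 0.8 (SD 0.632), 11 and 41. With linear gain both contrasts are 0.8 and give the same answer.

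**The case against.** The last treatment could mean the last double-blind session. The active-versus-sham label fits only that period, and on this reading the first window is the week-2 contrast. But section 12.0 does not say so, and sections 10.0 and 18.0 put the end of treatment at week 4. Even on this reading the follow-up window remains mislabelled and the term needs a definition.

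The design sections state the two-week control and the 24-versus-48-session exposure openly, so the label may be shorthand for the randomised arms, and weekly ratings mean a repeated measures model probably includes week 2. That is fair, but an omnibus test over weeks 0–4 or longer does not isolate week 2.

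The power figures rest on assumed inputs. The starkest losses come from a two-point week-4 test, not the full repeated measures model, and with full catch-up the nine-rating test does slightly better than week 2 alone (57% v 55%). The matching 56% depends on the shapes chosen: over weeks 0–4, late-only differences of (0, 0, 0, 0.4, 0.4) and (0, 0, 0, 0.8, 0.8) give 22% and 76%. These points stand, and the figures should be read only as showing the range.

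Finally, this is a largely descriptive pilot with no decision rule tied to the test. That limits the seriousness. However, Aim 1 is framed as a test of efficacy, and section 12.0 intends the effect size for later planning, so the contrast it estimates has to be stated.

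**Conclusion.** The point holds and should be fixed. From the documents alone, the follow-up window is mislabelled under every reading. On the natural reading of the last treatment (week 4), the first window also runs two weeks past the end of sham control and ends on a four-versus-two-week comparison. On that reading, the one contrast that estimates the effect against sham is left unnamed.

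The numerical consequence is not fixed. It ranges from none (linear gain, or no catch-up) to a later-trial size of 80 rather than 21 per arm (half catch-up, r = 0.6), or to an apparent effect where none exists under sham control (late-only benefit). The documents give no effect size, correlation or trajectory with which to choose among these. The fault lies in the label and the missing contrast; the randomised data remain sound. The timeline that section 10.0 refers to is a figure that was not available, so the rating schedule was judged on the text only.

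**What to change.** In section 12.0:

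1. Name active versus sham change from baseline to the end of week 2, rated before the first open-label session, as the Aim 1 efficacy contrast and as the sham-controlled effect size for planning later trials.
2. Label the week-4 and follow-up between-arm contrasts as four versus two weeks of active stimulation (immediate versus delayed start), and assign them to Aim 2, which otherwise has no analysis.
3. Define the last treatment, and list the time points in each repeated measures model.
4. Reconcile the rating schedules in section 1.0 (Aim 1), section 4.0 and section 10.0, so that the week-2 on-treatment rating is unambiguous and all times count from the same origin.

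The cost is analysis-plan wording and one schedule reconciliation. No visits or patients are added: Aim 1 and section 10.0 already provide for weekly ratings.

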**10.0 Study Design / Methods**

- Please see the study timeline above. Potential subjects will be phone screened and if appropriate scheduled for a consent meeting and then baseline assessments. They will then be given the video showing how to use the device. MUSC research assistants will then ship a device (and urine pregnancy test) to subjects. They will then have a training session online with MUSC RA's. Then, for each session initially they will do this online with MUSC RA's watching and rating and assisting if needed. They will complete a checklist of how well the subject administers the device. After three sessions if the subject is competent, they will self administer the device after that if they wish. All subjects can ask to have the RA online during any and all treatments if they wish. All sessions are immediately put into the database and the MUSC RA will daily monitor this and make sure the subject has correctly performed the session with no adverse events. If a subject misses a session the RA will call and talk about this. There will be immediate questions before and after each session, as well as the weekly online battery. There are also weekly online assessments and at 4,6,8 and 12 weeks after study start.

*Procedures performed to lessen the probability or magnitude of risks.*

We are excluding subjects with strokes or who are hemodynamically unstable. All sessions will be seated or even reclined if there are problems. Initial sessions are done with the MUSC RA and Soterix staff online. All session data and heart rate are sent immediately to the database and will be checked daily by research staff.

*How all drugs and devices will be used in the research (e.g. dose, dosage form, etc.)*

The device is taVNS applied to the left or right ear at two times the amplitude for perceptual threshold. This intensity of taVNS has been

used in MUSC IRB 1 monitored studies in Parkinson's Disease, Stroke Patients, Newborns and healthy volunteers. The dose for each session is *25Hz, 500us pulse width, 60s ON, 30s OFF, 1 hr. duration.*

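### Section 12.0 says 15 + 15 patients can detect a large or moderate effect; if moderate means 0.5 SD, the 24 planned completers give roughly 19–45% power under any plausible repeated measures ANOVA layout

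*Combined protocol and SAP*

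**What the plan says.** All references are to the combined protocol and SAP.

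- **Power statement (section 12.0, power paragraph).** After remarking that the lack of earlier data makes a formal calculation difficult, the plan states: "The repeated measures design in 15 active and 15 sham patients will allow us to detect differences with a large or moderate effect size". The sentence ends by saying that the effect size will serve to plan later trials. No significance level, target power, SD, correlation or effect metric is given.
- **Numbers (section 6.0, repeated in Aim 1).** "We will recruit 30 COVID positive adults in order to have 24 completers".
- **Analysis (section 12.0).** The stated intention is to: "compare the group changes in neuropsychiatric questionnaires in active versus sham taVNS using repeated measures ANOVA from baseline to immediately after last treatment". The same comparison is also planned over the 3-month follow-up.
- **Control period (Aim 1).** "After the controlled 2-week period, all participants will continue in a 2-week open label arm". Under Aim 2 and section 10.0, every patient receives active stimulation in weeks 3 and 4, so the last treatment falls at week 4.
- **Visits.** Aim 1: "These online ratings will be obtained at baseline, taVNS treatment weeks 1-4". Section 10.0: "There are also weekly online assessments and at 4,6,8 and 12 weeks after study start". Section 4.0 gives a list without week 1: "will be obtained at baseline, 2, 3, 4, 5, 6, 8 and 12 weeks after treatment".
- **Status (section 4.0, Primary Outcome).** "As this is a pilot and exploratory study, the outcomes are largely descriptive".

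**The concern.** The sentence claims that the trial can detect effects of a given size, but the plan contains nothing from which that claim can be checked. It also rests on the number enrolled, while the plan itself expects one patient in five to be lost (6 of 30). Two arms of 12 to 15 are small for a between-arm effect of half an SD, and only the first two weeks compare active with sham.

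What is at stake is how the result is read. Aim 1 sets out to test efficacy as well as feasibility, and Aim 2 says that the data will support an application for a later trial. A reader who trusts the power sentence could take a non-significant comparison as evidence against a moderate effect, when the confidence interval would still include one.

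**Working it through.** **Inputs from the plan.** 15 per arm enrolled; 24 completers, hence 12 per arm if losses are equal; repeated measures ANOVA; blinded weeks 1–2; last treatment at week 4. The plan gives no numerical power figure to reproduce.

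**Assumptions, none in the documents.** Moderate d = 0.5 SD and large d = 0.8 SD (SD of the score at one visit); two-sided 5%; correlation r = 0.5 to 0.7 between any two visits (compound symmetry); the same effect at weeks 1 and 2.

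**Formulas, n per arm.**

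- *Change contrasts (1 df):* t-test with 2n − 2 df and noncentrality (d/√v)·√(n/2). The variance of change is v = 2(1 − r) for week 2 minus baseline, and v = 1.5(1 − r) for the mean of weeks 1–2 minus baseline.
- *Omnibus group-by-time test over m visits:* noncentral F with m − 1 and (m − 1)(2n − 2) df and λ = 2n·Σ(δ − δ̄)²/[4(1 − r)], where δ is the between-arm difference at each visit.

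Example: n = 12, r = 0.5, differences 0, 0.5, 0.5 at baseline and weeks 1–2. Then Σ(δ − δ̄)² = 0.1667 and λ = 24 × 0.1667/(4 × 0.5) = 2.0. With 2 and 44 df, power is 21.3%.

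**Power for 0.5 SD (r = 0.5 to r = 0.7).**

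| Layout | 12 per arm | 15 per arm |
|---|---|---|
| Baseline and week 2 | 21.6–32.7% | 26.2–40.0% |
| Omnibus, baseline and weeks 1–2 | 21.3–33.2% | 26.1–41.1% |
| Mean of weeks 1–2 minus baseline | 27.2–41.5% | 33.3–50.4% |
| Omnibus, baseline to week 4, difference persists | 19.1–30.4% | 23.5–38.1% |
| Omnibus, baseline to week 4, difference vanishes after week 2 | 27.5–44.7% | 34.4–55.3% |

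The last two rows follow section 12.0's wording most closely. If the 24 completers split 9 and 15, the omnibus test over baseline and weeks 1–2 has 20–31%.

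**Power for 0.8 SD, blinded weeks.** At 12 per arm: 47–68% (week 2), 49–72% (omnibus), 58–80% (mean of both weeks). At 15 per arm: 56–78%, 59–82% and 69–88%.

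**Difference detectable with 80% power, 12 per arm.** The standardised change needed is 1.197, multiplied by √v:

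- Week 2: 1.197 × 1.000 = 1.20 SD (r = 0.5); 1.197 × 0.775 = 0.93 SD (r = 0.7).
- Mean of weeks 1–2: 1.197 × 0.866 = 1.04 SD; 1.197 × 0.671 = 0.80 SD.

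**95% CI half-width, 12 per arm:** 2.074 × √(2v/12).

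- Week 2: 0.85 SD (r = 0.5); 0.66 SD (r = 0.7).
- Mean of weeks 1–2: 0.73 SD; 0.57 SD.

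**The other reading, f = 0.25.** Over three visits λ = f²·N·m/(1 − r). With N = 24 and r = 0.5 this is 0.0625 × 24 × 3/0.5 = 9.0. Power is 74–93% for 24 patients and 84–97% for 30. For differences 0, d, d, f² = d²/18, so f = 0.25 means d = 0.25 × √18 = 1.06 SD, and d = 0.5 SD is f = 0.118.

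**The case against.** **The effect metric is undefined.** This is the strongest point. On the f = 0.25 reading the sentence is about right at the 30 patients it cites. A reader might infer from the table that the claim is false; the documents do not go that far. They never say what moderate means, so the claim can be shown to be unsupported under the usual 0.5 SD meaning, but not strictly refuted. The ambiguity is itself a reason to state the metric.

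**No single power figure belongs to the plan's ANOVA.** A reader might take 21–33% as the power of the planned analysis. Section 12.0 runs its ANOVA to the last treatment, at week 4, and does not say which term is tested. The honest figure is the range across layouts. That range stays far below 80%, and it does not depend on whether week 1 is rated.

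**Better analyses or a higher correlation would help.** Baseline adjustment using both blinded weeks, which the plan does not name, gives 38–50% at 12 per arm and 46–60% at 15. The omnibus test over baseline and weeks 1–2 reaches 80% for 0.5 SD only if r is about 0.90 (12 per arm) or 0.88 (15).

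**It is a pilot.** The outcomes are called largely descriptive, the power sentence looks ahead to later trials, and no decision hangs on a significance test. This stands, and it lowers the importance. A reader might conclude that the trial is too small for its purpose; the documents do not support that, because feasibility and safety lead the outcomes. The pilot wording nevertheless leaves the detection claim in place.

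**Conclusion.** The point holds in a limited form. Section 12.0 states a capability without the assumptions needed to support it, and on a larger number of patients than the plan expects to complete. For 0.5 SD, power is about 19–45% at 12 per arm and about 23–55% if all 30 contribute. Detection of 0.8 SD is not secure either: with 12 per arm in the blinded weeks, power just reaches 80% only for the mean of both weeks at r = 0.7.

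These figures rest on assumed values: two-sided 5%, r of 0.5–0.7, compound symmetry and an equal effect at both blinded weeks. Two facts need no assumption: the effect metric is missing, and the sentence counts 30 patients where 24 completers are planned. For a descriptive pilot the importance is modest, but the sentence should be corrected.

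**What to change.** Delete the word moderate, or define the metric behind both effect labels. Base the sentence on 24 completers, and replace the detection claim with precision and a detectable difference for the blinded comparison. For example:

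> Assuming two-sided 5%, 12 completers per arm and a between-visit correlation of 0.5–0.7, the active–sham difference in change over the 2-week blinded phase will be estimated with a 95% CI half-width of about 0.57–0.85 SD. Power of 80% is reached only for differences of about 0.8–1.2 SD. The study is not powered for 0.5 SD; estimates with confidence intervals will inform later trials.

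The ranges cover both week 2 alone and the mean of weeks 1–2, so the wording does not commit the sponsor to an omnibus test. It does require the blinded-phase difference to be reported, which uses data already being collected. No patients or visits are added. The cost is a less favourable stated capability.

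Separately, the visit list in section 4.0 should be reconciled with Aim 1 and section 10.0 on whether week 1 is rated.
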